2.1 ELIGIBILITY CRITERIA

2.1.1 Inclusion Criteria

- 2.1.1.1 Patients must have histologically confirmed desmoid tumor confirmed by the Laboratory of Pathology, NCI, that has progressed after receiving at least one line of standard treatment and that is not amenable to surgical resection or definitive radiation therapy.
- 2.1.1.2 Willingness to provide blood samples and 10 unstained slides or a tumor block for genetic research studies.
- 2.1.1.3 Any line of therapy with prior desmoid therapy, including radiotherapy, should have been completed at least 2 weeks before study entry and all toxicities must have resolved at least to eligibility levels.
- 2.1.1.4 Age ≥18 years; because no dosing or adverse event data are currently available on the use of Nirogacestat in patients <18 years of age, children are excluded from this study, but may be eligible for future pediatric trials.
- 2.1.1.5 ECOG performance status <2 (see Appendix A).
- 2.1.1.6 Life expectancy > 3 months.
- 2.1.1.7 Patients must have normal organ and marrow function as defined below:

absolute neutrophil count $\geq 1,500/\text{mcL}$ platelets $\geq 100,000/\text{mcL}$

total bilirubin $\leq 1.5 \text{ X}$ institutional upper limit of normal AST(SGOT)/ALT(SGPT) $\leq 5 \text{ X}$ institutional upper limit of normal

creatinine < 1.5 X institutional upper limit of normal

OR

creatinine clearance $\geq 60 \text{ mL/min/1.73 m}^2 \text{ for patients with}$

creatinine levels >1.5 mg/dL

hemoglobin $\geq 9 \text{ g/dL}$

2.1.1.8 Patients must be able to swallow whole tablets or capsules with no GI condition affecting absorption; nasogastric or G-tube administration is not allowed.

- 2.1.1.9 The effects of Nirogacestat on the developing human fetus are unknown. For this reason and because γ-secretase inhibitors are known to be teratogenic, women of child-bearing potential and men must agree to use adequate contraception (hormonal or barrier method of birth control; abstinence) for the duration of study participation and for at least 6 months after dosing with study drugs ceases. Should a woman become pregnant or suspect she is pregnant while she or her partner is participating in this study, she should inform her treating physician immediately. Men treated or enrolled on this protocol must also agree to use adequate contraception for the duration of study participation, and 6 months after completion of study drug administration.

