2.2 SCREENING EVALUATION

- 2.2.1.1 Histologic confirmation: A block or stained slides of tumor tissue from each participant to confirm diagnosis. All patients will be required to submit a tumor block or 10 unstained slides for genetic research purposes.
- 2.2.1.2 History and physical examination: Complete history and physical examination (including height, weight, vital signs, performance score, EKG) will be conducted within 72 hours prior to enrollment.
- 2.2.1.3 Imaging Studies (Baseline): Every participant should have an evaluation of known sites of disease as part of the baseline evaluation. All patients will be required to undergo a CT scan of the area of known disease; an MRI with diffusion weighting may be performed prior to start of study treatment, at the end of cycle 1, and at the time of restaging, per PI's discretion.
- 2.2.1.4 Laboratory Evaluation: Baseline laboratory data are to be obtained within 72 hours prior to enrollment:
 - Hematological Profile: CBC with differential.
 - Biochemical Profile: albumin, alkaline phosphatase, total bilirubin, BUN, calcium, creatinine, phosphorus, SGOT[AST], SGPT[ALT], magnesium, potassium, and sodium.
 - Coagulation Profile: PT, PTT, INR
 - Urine and/or serum pregnancy test for female participants of childbearing potential.

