3 STUDY IMPLEMENTATION

3.1 STUDY DESIGN

This is an open-label Phase II trial of Nirogacestat. Study drug will be administered at 150 mg, orally, BID, continually, in 21-day cycles.

Labs (CBC with differential and serum chemistries, including electrolytes) will be monitored each week during cycle 1, and then every other cycle. History and physical examination will be performed before the start of every other cycle. For patients having a history and physical examination performed by their local physician, study drug will be held until receipt of results; this may result in an interruption of therapy. For patients on study for more than a year, history and physical examination and labs can be performed every 3 cycles (up to 2 weeks before the start of the cycle). EKG monitoring will be performed at baseline and then post-drug administration on study day 1. Additional EKG monitoring may be performed during cycle 1 as clinically indicated.

Response assessment will be performed using RECIST 1.1. Restaging scans (CT scans of the known site of disease) will be performed at baseline prior to starting study treatment and then every 6 cycles (+/- 1 cycle) as described in Section 5.5. An MRI with diffusion weighting may be performed prior to start of study treatment, end of cycle 1, and at the time of restaging, per PI's discretion.

Health-related quality of life (HRQOL)/symptom questionnaires will be administered at baseline and at restaging (response assessment) as described in Section 3.4.

Archival unstained slides or tumor block will be sent for genetic research studies as described in Section 5.4.

Blood for research (whole exome sequencing) will be collected at baseline as described in Section 5.2.

Optional tumor biopsies for research purposes will be performed at baseline prior to study treatment and at the beginning of cycle 7 (+/- one cycle) as described in Section 5.2.

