3.5 STUDY CALENDAR

Baseline history and physical exam are to be conducted within 1 week prior to start of protocol therapy; laboratory evaluations must be done within 72 hours prior to start of protocol therapy. Scans and x-rays must be done ≤ 28 days prior to the start of therapy. The duration of a cycle will be 21 days (\pm 1 day for scheduling). The start of the next cycle may be delayed for up to 1 week to accommodate scheduling conflicts. History and physical examination and laboratory

Version Date: 5-18-2023

evaluations can be performed before the start of a cycle. For patients having their history and physical examination performed by their local physician, study drug will be held until receipt of results. For patients on study for more than a year, history, physical examination, and labs can be performed every 3 cycles (up to 2 weeks before the start of the cycle).

Version Date: 5-18-2023

	Pre- Study	C1 W1 (D1-7)	C1 W2 (D8-14)	C1 W3 D15-21)	C2 W1 (D1-7)	C2 W2 (D8-14)	C2 W3 (D15-21)	C3 W1 on	Off Treat- ment
Nirogacestat (PF- 03084014) ^a		X	X	X	X	X	X	X	
Informed consent	X								
Demographics	X								
Medical history	X								
Concurrent meds	X	X						X	
Physical exam ^b	X							X	X
Vital signs ^b	X							X	X
Height	X								
Weight b	X							X	X
Performance status ^b	X							X	X
CBC w/diff, plts ^c	X		X	X				X	X
Serum chemistry ^c	X		X	X				X	X
Coagulation profile	X								
Adverse event evaluation		X						X	X
Tumor measurements d	X								X
B-HCG ^e	X								
EKG ^f	X								
Tumor biopsies g	X								
Archival tissue h									
PG blood sampling h	X								
Questionnaire i	X								

- a. PF-03084014 twice daily in 21-day cycles.
- b. Should be performed on day 1 at the Clinical Center, and then at the start of every other cycle at the Clinical Center or by patient's local physician. For patients on study more than a year, history and physical examination can be performed every 3 cycles (up to 2 weeks before the start of the cycle).
- c. Serum chemistry (albumin, alkaline phosphatase, total bilirubin, BUN, calcium, creatinine, glucose, phosphorus, magnesium, potassium, SGOT [AST], SGPT [ALT], sodium) and CBC w/diff, platelets should be performed within 72 hours before enrollment (pre-study) and weekly during cycle 1, at the start of every other cycle and as clinically indicated. For patients on study more than a year, labs can be performed every 3 cycles (up to 2 weeks before the start of the cycle).

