- d. Tumor measurements are repeated every 6 cycles (±1 cycle). Documentation (radiologic) must be provided for patients removed from study for progressive disease. Optional MRI scans may be performed prior to start of study treatment, end of cycle 1, and every 6 cycles.
- e. Serum or urine pregnancy test (women of childbearing potential) within 1 week prior to enrollment

- f. EKG at baseline and then post-drug administration on day 1. Additional monitoring may be performed during cycle 1 as clinically indicated.
- g. Tumor biopsies are optional at baseline and at the beginning of cycle 7
- h. Archival tumor biopsy tissue and blood sample for pharmacogenomic analysis collected at baseline
- i. Quality-of-life questionnaire to be administered at baseline and at restaging

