3.6 CRITERIA FOR REMOVAL FROM PROTOCOL THERAPY AND OFF STUDY CRITERIA

3.6.1 Criteria for removal from protocol therapy

In the absence of treatment delays due to adverse event(s), treatment may continue until one of the following criteria applies:

- Disease progression,
- Intercurrent illness that prevents further administration of treatment
- Significant toxicity occurs despite 2 dose reductions as described in Section 3.3 or no lower dose level exists
- Pregnancy
- Patient decides to withdraw from the study
- General or specific changes in the patient's condition render the patient unacceptable for further treatment in the judgment of the investigator.

Patients will be followed for 30 days after the last dose is administered or until one of the following occurs: patient enrolls on another protocol, patient receives standard of care, or death, whichever comes first. The follow-up will consist of a phone call between Days 27-30 after the last dose to evaluate adverse events that were ongoing and any new events that might be deemed related to the therapy. Toxicities felt to be possibly, probably, or definitely related to the study drugs that have not resolved or stabilized by Day 30 post-treatment will be followed until stabilization or resolution via phone calls as clinically indicated.

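### The only scheduled pregnancy test is before enrollment; none is scheduled during open-ended treatment with a drug class the protocol calls teratogenic

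*Combined protocol and SAP*

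**What the plan says.** Pregnancy testing appears in three places, all before treatment. Section 2.2.1.4 lists, among the baseline labs, a "Urine and/or serum pregnancy test for female participants of childbearing potential". The B-HCG row of the calendar in section 3.5 is marked under Pre-Study only. Footnote e to that row reads: "Serum or urine pregnancy test (women of childbearing potential) within 1 week prior to enrollment".

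Labs during treatment are blood counts and chemistry. Footnote c sets them before enrollment "and weekly during cycle 1, at the start of every other cycle and as clinically indicated", and then relaxes the schedule: "For patients on study more than a year, labs can be performed every 3 cycles". Neither footnote c nor section 3.1 includes a pregnancy test among them.

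On the hazard, section 2.1.1.9 says that γ-secretase "inhibitors are known to be teratogenic, women of child-bearing potential and men must agree to use adequate contraception", and asks a woman who is or may be pregnant to tell her physician immediately. On duration, section 3.6.1 says that "treatment may continue until one of the following criteria applies"; the list that follows includes progression and pregnancy but no maximum time. Section 8.5.1 requires immediate discontinuation, reporting within 24 hours and follow-up of the outcome.

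**The concern.** The rules for stopping the drug and reporting a pregnancy begin to work only when somebody knows of it. If contraception fails and the woman does not suspect it, a team that follows the calendar exactly can keep dosing with no scheduled test to reveal the pregnancy.

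Suspicion may also be blunted. In the Phase I trial (section 1.2.2, Table 1), treatment-related nausea was reported in 23 + 1 = 24 of 64 patients, vomiting in 14 + 1 = 15 and fatigue in 19, so early symptoms of pregnancy could be put down to the drug. That is an inference, not something the documents report. Exposure can also be long: section 13.1.1 mentions participants elsewhere in the drug program still on treatment up to 1448 days after a skin cancer diagnosis.

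What is at stake is fetal exposure, not the response analysis. It concerns the women of childbearing potential among 17 planned patients. The protocol does not give their number, so the range is 0 to 17.

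**Working it through.** No design figure is involved, so there is nothing of the plan's own to reproduce. The check has two parts.

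**1. Is the blank B-HCG row a real omission, or just a sparse table?** Several calendar rows lack on-treatment marks, so the grid alone is not decisive. The footnotes settle it:

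| Row (footnote) | Marks in the grid | Later times in the footnote |
|---|---|---|
| Tumor measurements (d) | Pre-Study, Off Treatment | Every 6 cycles, ±1 |
| EKG (f) | Pre-Study | After dosing on day 1; more in cycle 1 if indicated |
| Questionnaire (i) | Pre-Study | At each restaging |
| B-HCG (e) | Pre-Study | None |

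For example, footnote f says "EKG at baseline and then post-drug administration on day 1". Footnote e has no such addition. The allowance in footnote c for extra labs when clinically indicated covers counts and chemistry, not B-HCG. Nothing forbids an unscheduled pregnancy test; the point concerns scheduled ones.

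**2. How many tests would the existing lab schedule carry?**

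Inputs: 21-day cycles (section 3.5); labs at the start of every other cycle, and every 3 cycles after one year (footnote c). The cycle 1 draws are left out.

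- Start of cycle n = day 21(n − 1) + 1. So C3 = 21 × 2 + 1 = day 43, C17 = 21 × 16 + 1 = day 337, and C19 = 21 × 18 + 1 = day 379.
- Year 1 (days 1–365): C3, C5, C7, C9, C11, C13, C15, C17, which is (17 − 3)/2 + 1 = **8 tests**. Nominal gap 2 × 21 = 42 days.
- Year 2 (days 366–730), every 3 cycles, nominal gap 3 × 21 = 63 days. Counting on from C17: days 400, 463, 526, 589, 652, 715. Counting from C19: days 379, 442, 505, 568, 631, 694. **6 tests** either way.
- Off Treatment: **1 test**.
- Current plan: **0** at all of these.

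Actual gaps can exceed the nominal ones, because section 3.5 allows cycle delays and allows labs before a cycle begins. It does not say how these combine, so no maximum is given. The expected number of undetected pregnancies cannot be calculated: the documents give neither the number of women at risk nor a contraceptive failure rate.

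**The case against.** The strongest objection is that this argues from absence while relevant text could not be read: part of section 13.1.1, text around the start of section 5.2, Appendix B and the consent pages. References 34 and 35, on hormonal effects on hair, are cited nowhere in the available text, which suggests that the unread part of section 13.1.1 deals with hormone-related effects. Related monitoring might be there. This stands as a limit on confidence. It does not remove the point, because the calendar and footnote e can be read, and staff would schedule tests from them.

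Second, the risk is already managed in layers: pregnant women are excluded, a test is done at entry, contraception is mandatory during the study and for 6 months afterwards, suspected pregnancy must be reported, history and examination recur, and the team discusses each patient weekly (section 7.6.1). No rule is broken. All of that is correct, and it makes this a missing back-up rather than an unmanaged hazard.

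Third, the remedy is partial and its benefit unmeasured. Counting tests is not counting harm averted, and gaps of 42 or 63 days still leave weeks of possible exposure. That also stands: testing shortens undetected exposure without eliminating it. The entry-test windows differ as well (72 hours in section 2.2.1.4, 1 week in footnote e); that is a separate inconsistency.

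One possible argument on our side is not used. Section 13.1.4 says the drug induces CYP3A4, which might weaken hormonal contraception, but section 1.2.2 reports midazolam AUC up 58.9% in volunteers, which points the other way. The question is open.

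**Conclusion.** The concern holds. In the available text, pregnancy testing stops at enrollment while dosing with a class described as teratogenic has no fixed end. The size is 0 scheduled on-treatment tests against 8 in year 1, 6 in year 2 and 1 at Off Treatment if the test were attached to labs already due. It affects between 0 and 17 patients and leaves the primary analysis unchanged. The change should be made because it is cheap and fetal harm may be irreversible; the plan is not otherwise unsafe. The conclusion assumes that the unread text schedules no test. The counts assume cycles that run to time.

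**What to change.** Amend footnote e, and mark the B-HCG row under C3 W1 on and Off Treatment, so that women of childbearing potential have a urine or serum pregnancy test:

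- with the scheduled labs at the start of every other cycle from C3;
- every 3 cycles after one year on study;
- at Off Treatment.

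The weekly cycle 1 draws need not include it. When a local physician does the visit, the test can be done there and the result sent with the history and examination findings; section 3.1 already says that in this situation "study drug will be held until receipt of results; this may result in an interruption of therapy". The Off Treatment test cannot prevent exposure, but it lets the outcome follow-up in section 8.5.1 begin.

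The cost is wording in the calendar and footnote, an inexpensive test at existing visits, an occasional false positive that needs repeating, and possibly a longer hold at local visits if the test result arrives after the examination results. No new visit or staff is needed. If the unread part of section 13.1.1 already schedules tests, the calendar and footnote e should be brought into line with it.

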3.6 CRITERIA FOR REMOVAL FROM PROTOCOL THERAPY AND OFF STUDY CRITERIA

3.6.1 Criteria for removal from protocol therapy

In the absence of treatment delays due to adverse event(s), treatment may continue until one of the following criteria applies:

- Disease progression,
- Intercurrent illness that prevents further administration of treatment
- Significant toxicity occurs despite 2 dose reductions as described in Section 3.3 or no lower dose level exists
- Pregnancy
- Patient decides to withdraw from the study
- General or specific changes in the patient's condition render the patient unacceptable for further treatment in the judgment of the investigator.

Patients will be followed for 30 days after the last dose is administered or until one of the following occurs: patient enrolls on another protocol, patient receives standard of care, or death, whichever comes first. The follow-up will consist of a phone call between Days 27-30 after the last dose to evaluate adverse events that were ongoing and any new events that might be deemed related to the therapy. Toxicities felt to be possibly, probably, or definitely related to the study drugs that have not resolved or stabilized by Day 30 post-treatment will be followed until stabilization or resolution via phone calls as clinically indicated.

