3.6.2 Off-Study Criteria

Patients will be removed from this study for one of the following reasons: completed 30-day follow-up period, toxicities are unresolved but stabilized, patient enrolls on another protocol, or patient receives standard of care. The reason for study removal and the date the patient was removed must be documented in the medical record.

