6 DATA COLLECTION AND EVALUATION

6.1 DATA COLLECTION

All data will be kept secure. Personal identifiers will not be used when collecting and storing data. An enrollment log will be maintained in the regulatory binder/file which is the only location of personal identifiers with unique subject identification number.

All AEs must be recorded on the AE case report form.

All AEs, including clinically significant abnormal findings on laboratory evaluations, regardless of severity, will be followed until satisfactory resolution. AEs should be reported up to 30 days following the last dose of study drug.

An abnormal laboratory value will be considered an AE if the laboratory abnormality is characterized by any of the following:

- Results in discontinuation from the study
- Is associated with clinical signs or symptoms
- Requires treatment or any other therapeutic intervention
- Is associated with death or another serious adverse event, including hospitalization.
- Is judged by the Investigator to be of significant clinical impact
- If any abnormal laboratory result is considered clinically significant, the investigator will
 provide details about the action taken with respect to the test drug and about the patient's
 outcome.

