7.3 NCI CLINICAL DIRECTOR REPORTING

Problems expeditiously reviewed by the OHSRP/IRB in the NIH eIRB system will also be reported to the NCI Clinical Director/designee; therefore, a separate submission for these reports is not necessary.

In addition to those reports, all deaths that occur within 30 days after receiving a research intervention should be reported via email unless they are due to progressive disease.

To report these deaths, please send an email describing the circumstances of the death to the Clinical Director/designee at [contact] within one business day of learning of the death.

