8.2 ASSESSMENT OF SAFETY EVENTS

AE information collected will include event description, date of onset, assessment of severity and relationship to study product and alternate etiology (if not related to study product), date of resolution of the event, seriousness and outcome. The assessment of severity and relationship to the study product will be done only by those with the training and authority to make a diagnosis and listed on the Form FDA 1572 as the site principal investigator or sub-investigator. AEs occurring during the collection and reporting period will be documented appropriately regardless of relationship. AEs will be followed through resolution.

SAEs will be:

- Assessed for severity and relationship to study product and alternate etiology (if not related to study product) by a licensed study physician listed on the Form FDA 1572 as the site principal investigator or sub-investigator.
- Recorded on the appropriate SAE report form, the medical record and captured in the clinical database.
- Followed through resolution by a licensed study physician listed on the Form FDA 1572 as the site principal investigator or sub-investigator.

For timeframe of recording adverse events, please refer to Section Error! Reference source not found. All serious adverse events recorded from the time of first investigational product administration must be reported to the sponsor.

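### Sections 3.6.1 and 3.6.2 can end post-treatment follow-up before Day 30 and limit new events on the call to possibly related ones, while Section 6.1 requires all adverse events up to 30 days after the last dose

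*Combined protocol and SAP*

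**What the plan says.** **Length of follow-up.** Section 3.6.1 follows patients for 30 days after the last dose, or until "patient enrolls on another protocol, patient receives standard of care, or death, whichever comes first". Section 3.6.2 lists, beside completion of the 30 days, further reasons for removal from the study: "toxicities are unresolved but stabilized, patient enrolls on another protocol, or patient receives standard of care".

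**Content of follow-up.** Under Section 3.6.1 the follow-up is a telephone call between Days 27 and 30, "to evaluate adverse events that were ongoing and any new events that might be deemed related to the therapy".

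**Reporting rules.** Section 6.1 requires every AE to go on the case report form and adds: "AEs should be reported up to 30 days following the last dose of study drug". It makes no exception for new therapy or another protocol and applies no relatedness filter. Section 8.2 says: "AEs occurring during the collection and reporting period will be documented appropriately regardless of relationship". The sentence in Section 8.2 that should point to the time frame is a broken cross-reference. Section 7.3 says: "all deaths that occur within 30 days after receiving a research intervention should be reported via email", with an exemption for deaths due to progressive disease.

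**Calendar.** The Section 3.5 table has an off-treatment column marked for AE evaluation, physical examination and laboratory tests. No day is attached to it.

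**The concern.** Staff who follow Section 3.6 as written can close out a patient before the Section 6.1 window has ended. On the call they can also leave out new events judged unrelated. Both actions comply with Section 3.6 and fall short of Section 6.1; the second also falls short of Section 8.2.

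What is at stake is the completeness of the safety data. In a trial of 17 planned patients, one patient is 1/17 = 5.9% of the safety population, so a single unrecorded late event would be visible in any tabulated rate. An event that is never collected cannot be recovered at analysis. One that is collected and later thought to reflect the next treatment can still be flagged. The primary response-rate analysis is not affected.

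**Working it through.** There is no stated figure to reproduce. The check sets the sections side by side and then does simple arithmetic on the window.

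**Step 1: the rules compared**

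| Item | Sections 3.6.1 / 3.6.2 | Reporting sections |
|---|---|---|
| End of window | Day 30, or earlier at another protocol, standard of care or death | 6.1: 30 days after last dose, no exception. 8.2: no window stated (broken reference) |
| New events | Only those that might be related | 6.1: all AEs. 8.2: any relationship, within the collection period |
| Deaths | No planned follow-up after a switch | 7.3: within 30 days of a research intervention, unless due to progressive disease |

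Stopping at death is not a conflict. The conflict in the window comes from the two switch triggers, and the conflict in scope comes from the wording of the call.

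**Step 2: can another section settle it?** Section 8.2 cannot, because its time-frame reference is broken. Section 7.4 mentions a reporting period for serious adverse events (SAEs) defined in Section 7.1, but Section 7.1 points to an external policy and gives no number of days. Section 6.1 is therefore the only place that states a general AE window in days.

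**Step 3: size for one patient.** Inputs are the 30-day window (Section 6.1), the call on Days 27-30 and the switch triggers (Section 3.6.1). Let d be the day after the last dose on which the patient switches, with d < 30.

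- Days of the Section 6.1 window without planned follow-up = 30 - d.
- d = 10: 30 - 10 = 20 days, 20/30 = 67% of the window.
- d = 3: 30 - 3 = 27 days, 27/30 = 90% of the window.
- If d < 27, follow-up has ended before the call window opens.

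The values of d are illustrations; the protocol gives no distribution of switch times.

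**Step 4: does the calendar close the gap?** The off-treatment column schedules an AE evaluation, so the call is not the only post-treatment assessment. Because it carries no date, it could take place at any point after the last dose, including before a switch. It does not secure information up to Day 30.

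**Step 5: how many patients?** The documents do not say how many of the 17 would switch before Day 27. The range runs from none to nearly all. Receipt of standard of care is also not defined. Section 1.2.1 notes that watchful waiting may be recommended in this disease, so staff could date this trigger differently.

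**The case against.** The strongest reply is that ending AE collection when a confounding treatment starts is a coherent choice, and that the 30 days in Section 6.1 can be read as an outer limit which Section 3.6.1 shortens. The first part stands as a matter of design: the protocol could adopt that rule. But Section 6.1 does not state it, and nothing tells staff that Section 3.6.1 overrides it.

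A second reply is that the SAE rules are independent of Section 3.6. All recorded SAEs go to the sponsor under Section 8.2, Section 8.3 sets 24 hours from awareness, and neither filters by relatedness. The death rule in Section 7.3 does not depend on on-study status. This is correct and limits the damage. These duties still depend on someone learning of the event, and after a switch no contact is planned.

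Several stronger readings are tempting, and the documents do not support them:

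- A reader might infer that the call is the only post-treatment contact. The calendar's off-treatment AE evaluation shows otherwise.
- A reader might infer that three sections each require all AEs and deaths to Day 30. Only Section 6.1 gives a 30-day AE window. Section 8.2 supplies scope without a window, and Section 7.3 exempts deaths from progressive disease.
- A reader might infer that SAEs and deaths will be under-counted, and selectively among patients who stop for progression or toxicity. No passage gives switch rates or says who switches soonest.
- A reader might infer that relatedness is decided before any event is collected. The threshold on the call is low, ongoing events are covered without it, and Section 8.1.5 still requires a relationship assessment for all AEs.

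**Conclusion.** The point holds as an internal contradiction with two parts. The switch triggers in Sections 3.6.1 and 3.6.2 can end follow-up inside the 30-day window of Section 6.1. The call's limit on new events is narrower than Sections 6.1 and 8.2 allow. Following Section 3.6 as written can lose AEs that Section 6.1 requires, and could leave reportable deaths unknown to the team.

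The size is 30 - d days for a patient who switches on Day d, with the call falling outside follow-up whenever d is below 27. The number of patients and events affected is unknown. The conclusion assumes that staff apply Section 3.6 literally and that the undated off-treatment evaluation is not routinely held at Day 30. It concerns safety ascertainment only and merits correction; it does not touch the response endpoint or the decision rule.

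**What to change.** Reconcile Sections 3.6.1, 3.6.2, 6.1, 7.3 and 8.2 so that one window governs AE and death ascertainment. To meet Section 6.1 as it stands:

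1. Keep the Day 27-30 call for every living patient who has not withdrawn consent, whether or not new therapy or another protocol has started.
2. Ask about all new AEs on that call, and assess relationship afterwards under Section 8.1.5.
3. Record the start date of any new therapy, so that later events can be flagged in the tables.
4. Repair the time-frame cross-reference in Section 8.2.

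If the sponsor instead intends collection to stop at new therapy, Section 6.1 must say so, the trigger must be defined, and the text must state how deaths covered by Section 7.3 will still be learned of. The call's limit on new events would still have to be squared with Sections 6.1 and 8.2.

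The cost is protocol wording and at most one telephone call per patient, which is already planned for those who do not switch. The small downside of the wider window is that some recorded events will be confounded by the next treatment; the recorded start date allows them to be separated.
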